#### 4. Genetic Testing N/A

##### A. Describe

- i. the types of future research to be conducted using the materials, specifying if immortalization of cell lines, whole exome or genome sequencing, genomewide association studies, or animal studies are planned
- ii. the plan for the collection of material or the conditions under which material will be received
- iii. the types of information about the donor/individual contributors that will be entered into a database
- iv. the methods to uphold confidentiality

**B.** What are the conditions or procedures for sharing of materials and/or distributing for future research projects?

**C.** Is widespread sharing of materials planned?

**D.** When and under what conditions will materials be stripped of all identifiers?

**E.** Can donor-subjects withdraw their materials at any time, and/or withdraw the identifiers that connect them to their materials?

- i. How will requests to withdraw materials be handled (e.g., material no longer identified: that is, anonymized) or material destroyed)?

**F.** Describe the provisions for protection of participant privacy

**G.** Describe the methods for the security of storage and sharing of materials

#### 5. **Subject Population:** Provide a detailed description of the types of human subjects who will be recruited into this study.

We will enroll 30 patients aged 50-80yrs (at least 50% over the age of 65) with tightly controlled ( $Hb_{A1c} < 8\%$ ), c-peptide-negative T1DM of  $>10$  years duration. Male and female subjects of all races and ethnicities will be targeted for study. Additional criteria will be BMI  $< 35$  kg/m^2 and a history of frequent hypoglycemia with unawareness (defined as 2 or more episodes of severe hypoglycemia within one year (requiring assistance) and 2 or more glucose values  $< 54$  mg/dL during a week of CGM (iPRO monitor, Medtronic) prior to enrollment. Hypoglycemia awareness will be assessed by detailed interviews and answering Ryan, Gold and Clarke questionnaires [78-80] that will be compared to hypoglycemic episodes recorded during blinded CGM. Exclusion criteria will be any significant medical comorbidities, significant alcohol intake and vegetarian diet since both are known to have an impact on counterregulation and brain metabolism [81, 82]. All inclusion and exclusion criteria are listed in the section below (Inclusion/exclusion criteria).

6. **Subject classification:** Check off all classifications of subjects that will be specifically recruited for enrollment in the research project. Will subjects who may require additional safeguards or other considerations be enrolled in the study? If so, identify the population of subjects requiring special safeguards and provide a justification for their involvement.

- |  |  |  |
|--|--|--|
|  Children              |  Healthy                           |  Fetal material, placenta, or dead fetus |
|  Non-English Speaking  |  Prisoners                         |  Economically disadvantaged persons      |
|  Decisionally Impaired |  Employees                         |  Pregnant women and/or fetuses           |
|  Yale Students         |  Females of childbearing potential |  |

NOTE: Is this research proposal designed to enroll children who are wards of the state as potential subjects? **Yes**  **No**

7. **Inclusion/Exclusion Criteria:** What are the criteria used to determine subject inclusion or exclusion?

Inclusion criteria:

- Provide signed and dated informed consent form
- Male or female
- Age 50-80 years (at least 50% over the age of 65)
- T1DM (>10 years duration)
- C-peptide undetectable
- HbA1c of < 8%
- History of frequent hypoglycemia with unawareness (defined as 2 or more episodes of severe hypoglycemia within one year requiring assistance) and 2 or more glucose values < 54 mg/dL during the week of Continuous Glucose Monitoring (CGM) (iPRO monitor, Medtronic) prior to enrollment
- BMI <35 kg/m^2
- Good general health as evidenced by medical history and blood screening
- Willing to comply with all study procedures and be available for the duration of the study
- Willing to fast for a limited time period on the morning of a clamp study

Exclusion Criteria

- Significant diabetic complications (untreated proliferative retinopathy, creatinine  $\geq 1.5$  mg/dl, urinary albumin levels 300 mg/day, autonomic neuropathy, painful peripheral neuropathy)
- Significant alcohol intake and vegetarian diet since both are known to have an impact on counterregulation and brain metabolism
- Any contraindications for MRI scanning, including presence of metallic implants or claustrophobia.
- Heavy exercise on a regular basis (i.e. marathon runners)

- Known allergic reactions to components of the study product(s)
- Treatment with another investigational drug or other intervention
- Active infection including hepatitis C, hepatitis B, HIV
- Any past or current history of alcohol or substance abuse
- Psychiatric or neurological disorders under active treatment
- Weighing less than 110 lbs
- Baseline hemoglobin < 10.5 g/dL in females, or < 12.5 g/dL in males.
- Blood donation within 30 days of the study
- History of coagulopathy or medical condition requiring long-term anticoagulant therapy (low-dose aspirin treatment is allowed)
- Co-existing cardiac, liver, and kidney disease
- Abnormal liver function tests
- Women who are pregnant (as assessed by pregnancy test that will be performed on female participants at reproductive age), planning to become pregnant, or lactating.
- Any medical condition or medication that, in the opinion of the investigators, will interfere with the safe completion of the study or study outcomes

8. How will **eligibility** be determined, and by whom?

Eligibility will be determined based on information collected at the screening visit after consent is obtained. This will include findings from physical examination, medical history, EKG, and laboratory testing in accordance with the inclusion and exclusion criteria listed above.

Eligibility to participate in the study will be determined by the licensed medical practitioners listed on this protocol (see personnel section).

9. **Risks:** Describe the reasonably foreseeable risks, including risks to subject privacy, discomforts, or inconveniences associated with subjects participating in the research.

- i. Intravenous catheters. The placement of intravenous catheters and/or the use of intravenous infusions can result in local hematoma formation or thrombophlebitis. Transient vasovagal symptoms including nausea, sweating, and lightheadedness may also occur during intravenous catheter placement.
- ii. Blood sampling. Same as above and frequent blood sampling may result in a drop in hematocrit levels.
- iii. Hyperinsulinemic hypoglycemic clamp technique. The hyperinsulinemic hypoglycemic clamp technique can result in hypoglycemia symptoms of varying severity. Subjects may experience autonomic symptoms including hunger, anxiety, tremor, palpitations, and/or diaphoresis. Others may experience fatigue, concentration difficulties, and/or mild confusion. The risk of plasma

glucose levels falling below the target value of  $50 \pm 3$  mg/dL is small but present; affected patients may experience exaggerated symptoms, as well as the development of dizziness, blurred vision, and/or confusion. All such symptoms would be rapidly reversible with an intravenous dextrose infusion.

- iv. Infusion of labeled acetate. Carbon-13 is a stable isotope of a naturally occurring substance. There are no known side effects associated with the administration of  $^{13}\text{C}$ -acetate, which has been safely used by our group here at Yale for many years.

Predictive low glucose suspend system (PLGS). The subjects enrolled in this study are T1DM patients at high risk of recurrent hypoglycemia who can largely benefit by a reduction in frequency, duration, and severity of hypoglycemia potentially achieved by using a PLGS system [83-85]. The main risk of the use of the PLGS pump system is a worsening of glycemic control, which could be an increased frequency of hyperglycemia or hypoglycemia.

- v. Magnetic resonance imaging/spectroscopy. The risks due to the magnet study are similar to clinical MRI. Radio frequency and magnetic fields to be used for  $^1\text{H}$  and  $^{13}\text{C}$  spectroscopy in this study present no known hazards to human subjects whose bodies do not contain any para-magnetic metals. Subjects will be questioned using the protocol developed by Diagnostic Imaging concerning heart pacemakers, metallic objects, IUDs, vascular clips, electrodes, cochlear implants, neurostimulators, shunts, heart valve implants, penile implants, vascular filters, rods & screws, post CABG pacer wires, colored contact lens, dental prostheses, limb prostheses, eye prostheses, shrapnel, metal in head, eye, or skin, and embolization coils. If they cannot be removed safely, the subject will be excluded from the study. Proton decoupling, which is used in  $^{13}\text{C}$  spectroscopy, presents the potential risk of tissue heating. However, the regional heat deposition will never exceed the FDA guideline of 4 watts/kg. In over 1,000 experiments to date using proton decoupling, we have not experienced any patient complaints about tissue heating.

- vi. Questionnaires: Some subjects may feel discomfort or distress in responding to certain items on the questionnaires.

**10. Minimizing Risks:** Describe the manner in which the above-mentioned risks will be minimized.

The primary risks to the subject are impact by magnetic objects accidentally brought into the magnet room, anxiousness, irritation due to the IV blood sampling, and hypoglycemia after the glucose infusion. The investigators in this protocol pioneered human infusion studies of stable isotope labeled metabolic substrates in MR systems and have been routinely performing these studies since 1988. Studies of brain metabolism using stable isotope infusion in the MRC have been performed since 1990. To date there have been no patient injuries during these studies and only minor adverse incidences (anxiety, IV irritation).

To confront the specific risks listed above:

- i. Intravenous catheters. Intravenous catheters will be placed under sterile conditions by experienced HRU staff members. All infused solutions will be prepared in sterile form by the YNHH pharmacy and will be tested for pyrogenicity and sterility prior to use. During dextrose infusions, 20%

dextrose will be used to reduce the risk of thrombophlebitis normally associated with the use of excessively hypertonic glucose solutions.

- (i) Blood sampling. No subject with a hematocrit less than 37% for males and less than 33% for females will be studied. Total blood loss (~515 cc) for each subject, spread over the screening visit and 2 study visits (8-10 weeks apart), will exceed the amount obtained during a typical blood donation by about 10%. People who are in good health are not usually affected by this kind of blood loss. To protect against adverse events, all patients with significant baseline anemia (see exclusion criteria) will be excluded from the study. All patients who have donated blood within 30 days of the study will be asked to wait 6 weeks before participating in the study. Study participants will undergo a hematocrit check prior to the second clamp visit. Should a value of less than 37% for males and less than 33% for females be measured, the second clamp will be postponed by at least 6 weeks, to ensure adequate recovery. Patients will be advised to refrain from blood donations for 8 weeks after study completion. All subjects will be given a telephone number to enable immediate communication with the PI or one of the co-investigators, to report any delayed adverse effects and to receive recommendations for treatment of any adverse effects.
- ii. Hyperinsulinemic hypoglycemic clamp technique. All study procedures, including the hyperinsulinemic clamp, will be performed under the direct supervision of a qualified, licensed practitioner. To avoid excess hypoglycemia during the hyperinsulinemic clamp, plasma glucose will be checked every five minutes using a bedside glucose monitor. Based on these measurements, the plasma glucose will be adjusted via the 20% dextrose infusion.
- iii. Infusion of unlabeled acetate. Stable isotope infusions will be prepared in sterile form by the YNHH pharmacy and will be tested for pyrogenicity and sterility prior to use. The MRRC has extensive experience with stable isotope infusions including BHB, glucose and lactate (HIC # 10605, [name] PI; HIC#1208010648, [name] PI) and to date there have been no adverse events due to the infusion.
- iv. PLGS system. The primary risk of PLGS therapy is worsening of glycemic control, either more frequent hyperglycemia or hypoglycemia. Both are frequent occurrences in people with type 1 diabetes, and by study design, the subjects enrolled will already have a history of frequent and/or severe hypoglycemia. Published studies of PLGS systems have not demonstrated an increased risk of hypo- or hyperglycemia using these devices. To minimize these risks:
  - iv.1 All subjects undergoing therapy with PLGS insulin therapy will have an in-depth training session with an experienced study nurse to adequately train the use of the system. Our study team has trained hundreds of subjects on the use of sensor-augmented pump therapy and over 30 subjects on the use of the specific system used in this application. Sensors will initially be placed by study nurses, and subjects will be trained on how to insert and remove them. Supplemental training materials will be available for use for subjects at home.
  - iv.2 All subjects will have weekly visits (in person or on the phone) with study nurses and physicians to review blood glucose logs and insulin doses, potential adverse events, and other clinical issues. Changes will be made to diabetes management as deemed necessary by study physicians/nurses.

- iv.3 All subjects will be able to reach study physicians/nurses at all times of day or night for urgent issues through the use of a dedicated cell phone carried by study physicians/nurses.
- iv.4 All subjects using CGM will be instructed to insert sensors using clean technique to minimize infection and irritations. Subjects will be instructed to assess skin sites at the item of sensor removal for irritation or infection and will call the study team as needed for further evaluation.
- v. Magnetic resonance imaging/spectroscopy. The primary risks to the subject from MRI are impact by magnetic objects accidentally brought into the magnet room, anxiousness, irritation due to the IV blood sampling, and hypoglycemia after the glucose infusion. The investigators in this protocol pioneered human infusion studies of stable isotope labeled metabolic substrates in MR systems and have been routinely performing these studies since 1988. Studies of brain metabolism using stable isotope infusion in the MRC have been performed since 1990. To date there have been no patient injuries during these studies and only minor adverse incidences (anxiety, IV irritation). To confront the specific risks listed above:
- v.1 All potential study subjects will also be screened for MR safety using the standard MR safety protocol developed by Yale New Haven Hospital's Diagnostic Imaging department. Subjects with claustrophobia, a history of panic attacks or with other contraindications to MR scanning will be excluded from the study. The MR safety screening process will be performed both during the screening interview and on the day of an MR study.
- v.2 Study subjects will be closely followed by an experienced clinical research team, including an experienced nurse with ACLS training who is with a patient at all times, a licensed MD, and an experienced MRS technologist. All personnel involved in the study will be trained in MR safety procedures. The MD and technologist who are outside of the room have direct visual contact with the subject and nurse through a window, a TV monitor, and audio contact through a speaker system. Subjects who become claustrophobic in the magnet will be removed immediately from the magnet room. Patients who experience distress in the magnet room for any reason including seizures, loss of consciousness, or pain will be removed from the magnet room in accordance with well-established procedures developed for the Magnetic Resonance Research Center. Should an emergency arise, the technologist will telephone the hospital emergency operator and have an ambulance with personnel trained in resuscitation sent to the MR Center. The other members will remove the patient via the detachable patient bed from the magnet room if immediate resuscitation is needed the physician present during the study will perform this procedure, using a fully equipped crash cart which will be in the console room during the study.
- vi. Questionnaires: All subjects will be able to speak to a study physician or nurse at any time if responding to certain questions produces discomfort and/or distress. Subjects will be referred to appropriate counseling and support if deemed appropriate by study physician/nurse.

All subjects will be given a telephone number to enable immediate communication with the P.I. or one of the co-investigators, to report any delayed adverse effects and to receive recommendations for treatment of any adverse effects.

11. **Data and Safety Monitoring Plan:** Include an appropriate Data and Safety Monitoring Plan (DSMP) based on the investigator's risk assessment stated below. (Note: the HIC will make the final determination of the risk to subjects.)

- a. What is the investigator's assessment of the overall risk level for subjects participating in this study?  
Moderate
- b. If children are involved, what is the investigator's assessment of the overall risk level for the children participating in this study?  
N/A
- c. Include an appropriate Data and Safety Monitoring Plan. Examples of DSMPs are available here <http://www.yale.edu/hrpp/forms-templates/biomedical.html> for
- i. Minimal risk
  - ii. Greater than minimal

The risks associated with the current study are deemed moderate for the following reasons: We do not view the risks associated with the combined use of insulin and dextrose as minimal. Given our experience with the combined co-administration of insulin and dextrose, we do not view the proposed studies as high risk. Although PLGS systems were not specifically tested in vulnerable older adults with T1DM, safety data collected in other populations are reassuring.

Although we have assessed the proposed study as one of moderate risk, the potential exists for anticipated and/or unanticipated adverse events, serious or otherwise, to occur since it is not possible to predict with certainty the absolute risk in any given individual or in advance of first-hand experience with the proposed study methods.

Therefore, we provide a plan for monitoring the data and safety of the proposed study as follows:

**Attribution of Adverse Events:**

Adverse events will be monitored for each subject participating in the study and attributed to the study procedures / design by the principal investigator [name] according to the following categories:

- a.) Definite: Adverse event is clearly related to investigational procedures.
- b.) Probable: Adverse event is likely related to investigational procedures.
- c.) Possible: Adverse event may be related to investigational procedures.
- d.) Unlikely: Adverse event is likely not to be related to the investigational procedures.
- e.) Unrelated: Adverse event is clearly not related to investigational procedures.

**Plan for Grading Adverse Events:**

The following scale will be used in grading the severity of adverse events noted during the study:

1. Mild adverse event
2. Moderate adverse event
3. Severe

**Plan for Determining Seriousness of Adverse Events:**

**Serious Adverse Events:**

In addition to grading the adverse event, the PI will determine whether the adverse event meets the criteria for a Serious Adverse Event (SAE). An adverse event is considered serious if it:

1. is life-threatening

2. results in in-patient hospitalization or prolongation of existing hospitalization
3. results in persistent or significant disability or incapacity
4. results in a congenital anomaly or birth defect OR
5. results in death
6. based upon appropriate medical judgment, may jeopardize the subject's health and may require medical or surgical intervention to prevent one of the other outcomes listed in this definition, or
7. adversely affects the risk/benefit ratio of the study

An adverse event may be graded as severe but still not meet the criteria for a Serious Adverse Event. Similarly, an adverse event may be graded as moderate but still meet the criteria for an SAE. It is important for the PI to consider the grade of the event as well as its "seriousness" when determining whether reporting to the HIC or HSC is necessary.

**Plan for reporting serious AND unanticipated AND related adverse events, anticipated adverse events occurring at a greater frequency than expected, and other unanticipated problems involving risks to subjects or others to the HIC or HSC.**

The investigator will report the following types of adverse events to the HIC or HSC:

- a) serious AND unanticipated AND possibly, probably or definitely related events;
- b) anticipated adverse events occurring with a greater frequency than expected; and
- c) other unanticipated problems involving risks to subjects or others.

These adverse events or unanticipated problems involving risks to subjects or others will be reported to the HIC or HSC within 48 hours of it becoming known to the investigator, using the appropriate forms found on the website.

**Plan for reporting adverse events to co-investigators on the study, as appropriate the protocol's research monitor(s), e.g., industrial sponsor, Yale Center for Clinical Investigation Research Subject Advocates (RSAs), Cancer Center's Quality Assurance, Compliance and Safety Committee (QUACS) Protocol Review Committee (PRC), DSMBs, study sponsors, funding and regulatory agencies, and regulatory and decision-making bodies.**

For the current study, the following individuals, funding, and/or regulatory agencies will be notified (choose those that apply):

- All Co-Investigators listed on the protocol.
- Yale Center for Clinical Investigation Research Subject Advocates (RSAs)

The principal investigator [name] will conduct a review of all adverse events upon completion of every study subject. The principal investigator will evaluate the frequency and severity of the adverse events and determine if modifications to the protocol or consent form are required.

- d. For multi-site studies for which the Yale PI serves as the lead investigator:
  - i. How will adverse events and unanticipated problems involving risks to subjects or others be reported, reviewed and managed?
  - ii. What provisions are in place for management of interim results?
  - iii. What will the multi-site process be for protocol modifications?  
N/A

**10 Statistical Considerations:** Describe the statistical analyses that support the study design.

To test the hypothesis that “*Strict avoidance of hypoglycemia for 8 weeks reduces frontal cortex C-acetate utilization by 25%*” a two-sided nonparametric Wilcoxon rank sum test will be used. SAS® statistical software, version 9.4, will be used to conduct data analyses.

Sample size estimation and power calculation have been conducted with PASS statistical software. [86, 87]. Sample size estimates are based on published human acetate data, as well as our previously published differences between control and RH animal studies [48, 56]. These differences correspond to a decrease of approximately 25% or more in brain acetate utilization in the group of T1DM patients undergoing the PLGS intervention. We estimate that sample sizes of 12 subjects per group will achieve 80% power to detect this 25% reduction with estimated group standard deviations of 0.18 and 0.10 in the respective control and intervention groups, using a two-sided Wilcoxon rank sum test and assuming a significance (alpha) level of 0.05. To adjust the sample size for possible missing values, three additional study participants will be enrolled per treatment group; we thereby estimate that a sample size of 15 per group will be adequate to test the proposed primary hypothesis.

SECTION II: RESEARCH INVOLVING DRUGS, BIOLOGICS, RADIOTRACERS, PLACEBOS AND DEVICES
--

*If this section (or one of its parts, A or B) is not applicable, state N/A and delete the rest of the section.*

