All participants will undergo MRS measurement of brain [2-C]-acetate metabolism under controlled hypoglycemia (hyperinsulinemic hypoglycemic clamp) before and after the 8-week intervention (see Fig.5B). To determine the effect of strict hypoglycemia avoidance in the intervention group we will measure brain acetate metabolite enrichment time courses, which will be fitted with our metabolic

model to determine whether acetate contribution to brain oxidative capacity is diminished. In addition, we will assess how counterregulatory epinephrine and glucagon responses under hypoglycemia are affected by the intervention. The day before each MRS session, cognitive performance and hypoglycemia awareness will be also assessed. Blood Volumes collected and Schedule of Events Tables are included at the end of this application (see Appendix 1-2).

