After completion of the first MRS session, subjects will randomized to either the intervention or control group. The intervention group consists of treatment with a PLGS-enabled insulin pump/CGM combination (Medtronic MiniMed 670G pump with Guardian sensor, or Tandem t:slim X2 pump with Dexcom sensor) in auto mode for Medtronic users and with Basal-IQ for Tandem users; subjects in the control group will use the same PLGS-enabled insulin pump/CGM combination but in manual mode for Medtronic users or without Basal-IQ for Tandem users. All subjects will undergo a PLGS system training session with a study nurse or nurse practitioner. Subjects will have weekly phone calls with study team members (physician and/or advanced practice nurse or registered nurse) to review blood glucose logs and insulin doses, potential adverse events, and other clinical or device-related issues. Subjects can also speak with a study physician, advanced practice nurse or registered nurse more frequently if there are any questions or concerns.

The two pump devices that will be used are: Medtronic MiniMed™ 670G system or Tandem t:slim X2 with Control IQ software. For subjects who use multiple daily injections as part of their standard insulin therapy or for subjects who do not use the MiniMed 670G pump or t:slim X2 pump, a loaner MiniMed 670G system will be provided. For subjects who use multiple daily injections as part of their standard insulin therapy, the training and support described above will be provided and may potentially be provided on a more frequent and/or intensive basis depending on the needs of the subject. A washout is not required given that regardless of method of administration (pump or injection), the insulin and dosages remain the same. Likewise, the risks remain similar. Furthermore, regardless

of the method of administration that the subject uses in their usual standard of care, all subjects will be trained and supported as much as is necessary in order to ensure that they understand how to use the PLGS system, and any subject who, in the opinion of the clinical study staff, is deemed to not be able to safely use the system will not continue in the study.

Program on Aging field core staff will remain in close contact with study participants via phone to identify and eliminate any obstacles to successful study completion.

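### The primary analysis names only an unadjusted rank-sum test with no effect estimate, although every participant has a pre-randomisation MRS value of the same outcome that could be used at almost no cost

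*Combined protocol and SAP*

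**What the plan says.** Section I, item 10 (Statistical Considerations) gives one analysis for the primary hypothesis: "a two-sided nonparametric Wilcoxon rank sum test will be used". It does not say whether the test is applied to follow-up values, changes or percentage changes. It mentions no covariate, no estimator and no interval.

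The sample size rests on the same test: "sample sizes of 12 subjects per group will achieve 80% power to detect this 25% reduction". The calculation takes as its inputs "estimated group standard deviations of 0.18 and 0.10 in the respective control and intervention groups" and is made "assuming a significance (alpha) level of 0.05". The control mean behind the 25% is not printed, nor is whether the SDs describe values or changes. On missing data the section says: "To adjust the sample size for possible missing values, three additional study participants will be enrolled per treatment group".

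Section I, item 3 (Research Plan) has acetate MRS under the hypoglycaemic clamp in all participants, both before and after the intervention. The time courses are to be fitted with the group's metabolic "model to determine whether acetate contribution to brain oxidative capacity is diminished". Subsection d) of the Research Plan fixes the order: "After completion of the first MRS session, subjects will randomized to either the intervention or control group".

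**The concern.** A baseline value of the primary outcome, measured before allocation, is the most natural covariate a trial can have. Here it is already budgeted for each participant, and the only named primary analysis makes no stated use of it. With 12 analysable participants per arm planned, unexplained between-person variation is costly.

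There is also an estimation gap. The hypothesis is quantitative, but a rank-sum p-value cannot tell the reader whether the reduction was near 25%, much smaller or much larger. In a trial of this size, the interval carries most of the information.

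Finally, the unnamed analysis variable leaves open choices with different power, including an analysis of unadjusted changes.

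**Working it through.** **Inputs from item 10.** 12 analysable per arm (15 enrolled), two-sided alpha 0.05, power 80%, SDs 0.18 (control) and 0.10 (intervention).

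**Assumptions the documents do not give.** Normal data; 0.18 and 0.10 are SDs of follow-up values; baseline SD 0.18; pre-post correlation r from 0 to 0.7.

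**1. The plan's 80%.** It cannot be reproduced from the printed inputs, because a 25% reduction has no absolute size without a control mean. Working backwards:
- root-mean-square SD = sqrt((0.18² + 0.10²)/2) = sqrt(0.0212) = 0.1456
- standard error of the difference = sqrt(0.0424/12) = 0.0594
- simulated rank-sum power is 80% at a difference of about 0.185, which implies a control mean of 0.185/0.25 = 0.74. Approximate formulas give about 0.17, a control mean near 0.67.

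If 25% instead means 0.25 on the SD scale, rank-sum power is about 97%, which does not match the stated 80%.

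**2. Effect of adjusting.** With equal correlation in both arms, adjustment multiplies the residual variance by 1 - r²: 1.00, 0.91, 0.75 and 0.51 at r = 0, 0.3, 0.5 and 0.7. Against this stand one degree of freedom and the caution of HC3 standard errors, chosen because the assumed SDs differ. Simulated power (%) at difference 0.185:

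| r in both arms | 0 | 0.3 | 0.5 | 0.7 |
|---|---|---|---|---|
| Rank-sum on follow-up, 12 per arm | 80 | 80 | 80 | 80 |
| HC3 ANCOVA, 12 per arm | 78 | 82 | 88 | 96 |
| Rank-sum on residuals from pooled regression on baseline, 12 per arm | 78 | 81 | 88 | 95 |
| Rank-sum on follow-up, 15 per arm | 89 | 89 | 89 | 89 |
| HC3 ANCOVA, 15 per arm | 89 | 91 | 95 | 99 |

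Before rounding, the HC3 gain over rank-sum at 12 per arm is about -2, +1, +8 and +15 points (15 to 16 at r = 0.7, depending on the run). At 15 per arm it is about 0 to +10. About 3 points of the gain at 12 per arm come from leaving ranks, since an unadjusted Welch test already has about 83%.

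**3. Unequal correlation.** With r = 0.5 in controls and 0 under intervention, HC3 ANCOVA has about 82%; with 0.3 and 0, about 80%. The gain is then about -1 to +2 points.

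**4. Larger effect.** At a difference of 0.25, with rank-sum already near 97%, the gain is at most about 3 points.

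**5. Unadjusted changes.** The two arms' change variances sum to 0.0424 + 2(0.18²) - 2r(0.18² + 0.18 × 0.10) = 0.1072 - 0.1008r. This falls below the follow-up sum of 0.0424 only when r exceeds 0.0648/0.1008 = 0.64. Rank-sum power on changes is about 43, 56, 69 and 87% at r = 0, 0.3, 0.5 and 0.7. A smaller baseline SD helps: at r = 0.5 it is 81% with SD 0.14 and 88% with SD 0.10. If 0.18 and 0.10 are already SDs of change, a change analysis has the stated 80% by construction.

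**6. Unusable baseline spectra.** Suppose two of 12 per arm (an assumed rate). Complete-case HC3 ANCOVA has 68, 72, 79 and 91%. Replacing the missing baselines with the mean of all observed baselines, blind to arm, gives 78, 81, 86 and 94%. The rank-sum test on all 12 keeps 80%.

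**7. Error rate and precision.** Simulated type I error is about 5% for rank-sum and 4% for HC3 ANCOVA. The 95% interval half-width is 0.134, 0.128, 0.117 and 0.099 at r = 0, 0.3, 0.5 and 0.7.

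**The case against.** The rank-sum test is valid under randomisation, makes few assumptions and is the test the sample size was built on. The power gain rests on inputs absent from the documents, and the top figure needs a correlation of 0.7 in both arms. The trial's own hypothesis makes that doubtful: if the intervention reverses the metabolic adaptation, baseline may predict follow-up poorly in treated participants, and the plan assumes a smaller SD there. In that case, or if the effect is 0.25 on the SD scale, there is little to gain. A Hodges-Lehmann shift with an interval would supply an estimate without changing the test. ANCOVA also brings a missing-baseline problem that the planned test, applied to follow-up values, does not have.

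All of this stands, and it limits the point to an improvement. It does not remove it: no section plans any estimate, and a Hodges-Lehmann interval on follow-up values would still leave the baseline unused. The loss if the baseline is uninformative is about 2 points against rank-sum (about 5 against Welch), and the imputation rule handles most of the missing-baseline problem.

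A reader might infer that the plan intends to test changes and is therefore badly underpowered. The documents do not support that. Talk of a decrease fits a comparison of follow-up values as well. The SDs are described by group, and the estimates come from published human data and differences between control and recurrent-hypoglycaemia animals, which points towards SDs of values without settling it.

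**Conclusion.** The point holds as an efficiency and estimation improvement. A pre-randomisation value of the primary outcome exists for every participant, the named primary analysis makes no stated use of it, and no effect estimate is planned.

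The power figures are illustrative. They depend on the assumed normality, control mean, baseline SD and correlation, and they range from a small loss to a worthwhile gain. Adjustment overtakes the rank-sum test once a common correlation exceeds roughly 0.2 to 0.3. The need for an estimate with an interval does not depend on any of these assumptions.

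Three stronger conclusions are tempting and are not supported: that the rank-sum test is wrong or biased, that the trial is underpowered, and that the stated 80% is false. The 80% cannot be checked without the control mean, which is not the same as being incorrect.

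**What to change.** - **Primary analysis.** Use ANCOVA of follow-up frontal acetate utilisation on arm and baseline value, raw scale, with HC3 or permutation inference. If a distribution-free test is preferred, apply the same rank-sum test to residuals from the pooled regression of follow-up on baseline.
- **Estimate.** Report the adjusted difference, also as a percentage of the adjusted control mean, with a 95% confidence interval.
- **Sensitivity analysis.** Keep the unadjusted rank-sum test on follow-up values, with a Hodges-Lehmann shift and interval.
- **Missing baseline.** Keep any participant with a follow-up spectrum but no usable baseline spectrum, imputing the mean of all observed baselines blind to arm.
- **Power paragraph.** State the analysed variable, the control mean, whether the SDs are of values or changes, and the assumed correlation. Do not use unadjusted changes unless the 80% is recomputed with an SD of change.

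The cost is about one paragraph of statistical text, one degree of freedom, about 2 points of power if the correlation is near zero, and the missing-baseline rule. No new data are needed.
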